Specific Aim 2: To examine the moderating effects of MCI on intervention efficacy. We will also test for moderation effects to determine at what stage along the cognitive status continuum—without MCI vs. MCI—intervention is most effective. To do so, we will examine three-way interactions (MCI x training group x time) for the CAP, cognitive, and everyday function composites. When an interaction is significant, we will stratify analyses by MCI status and examine effect sizes. Effect sizes from pre- to post- training relative to controls will be compared for participants with/without MCI. An alpha of .05 will be used for these analyses.

Participants who score 26 or higher on the MoCA will be defined as no MCI (i.e., cognitively normal). Those participants who score a 20-25 on the MoCA will be defined as MCI if they score a 0.5 on the CDR and have performance at or 1 SD below their age, sex, and education norms on any of the following measures: Trails, Verbal Fluency, Digit Coding, Craft Story Recall, Multilingual Naming Test, or Benson Complex Figure. Those with MoCA scores 20-25 who score 0 on the CDR, but have performance at or 1SD below expected for age, sex, and education will be adjudicated prior to analyses. If an individual scores 20-25 on the MoCA, and 0.5 on the CDR, but has performance above expected on all of the aforementioned measures, their case will be adjudicated prior to analyses. The study physicians will adjudicate such cases prior to coding of MCI status for final analyses.

To quantify the effects of piano training further, in addition to examining composite outcomes as detailed above, we will calculate and report effect sizes for pre-to-post change of piano training relative to controls for each individual measure of CAP, cognition, and everyday function for the sample overall as well as stratified by MCI status and among those who were adherent only (80% or more of sessions completed).

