In the primary analyses, we examined whether performance changed differentially by random assignment across composite outcomes from baseline to post-test as indicated by a significant group-by-time interaction. Covariates included hearing PTA, visual acuity, and expectations. The group-by-time interactions were not statistically significant for any of the outcomes ($ps > .194$). See Table 2. The results did not change when we included only those who were adherent ($ps > .180$). See Supplementary Table B. Piano training did not significantly enhance CAP, cognition, or everyday function as compared to music listening. We further examined if intervention effects varied by MCI status (Supplementary Table B). There were no significant group-by-time-by-MCI status interactions indicating those with and without MCI did not show differential benefit ($ps > .245$). Thus, MCI did not significantly moderate the effects of piano training.

Effect sizes for piano training as compared to music listening are shown in Table 3. Improvements were not evident in the primary analyses, adherent analyses, or the subsample without MCI on measures of CAP, cognition, or everyday function. Participants with MCI randomized to piano training showed potential small effect sizes for improvement relative to music listening on Trails A, Digit Symbol Coding, and one subtest of the TEA ($ds \geq 0.25$). Raincloud plots of individual assessment and composite variables are included in the supplemental materials.

Results indicated significant effects of time for ATTR in all models and significant effects of time for CAP in the primary and adherent analyses indicating improved performance from pre- to post- training. Significant effects of time were found for cognition and TEA in the primary and adherent analyses, indicating a tendency for decline across time. With respect to covariate effects, CAP, ATTR, and cognitive performance were significantly impacted by hearing. Similarly, Timed IADL and cognitive performance varied significantly by visual acuity. Those with poorer hearing or vision tended to perform worse on these outcomes. Interestingly,

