Hearing	-0.09	0.06	.134	-0.14	0.06	.016
Visual acuity	-6.55	5.33	.220	-15.45	5.12	.003
Expectations	-0.79	0.67	.234	-1.96	0.64	.003
	Timed IADL+			Test of Everyday Attention		
Intercept	48.89	1.32	<.001	62.34	1.15	<.001

Group	3.15	2.67	.240	1.37	2.33	.557
Time	0.14	0.79	.863	-8.61	0.67	<.001
Group x time	-1.53	1.58	.327	-0.40	1.340	.765
Hearing	0.07	0.57	.194	-0.02	0.05	.603
Visual acuity	12.75	4.770	.008	0.24	4.470	.957
Expectations	1.02	0.59	.089	-0.79	0.56	.157

Note. ATTR=Adaptive Tests of Temporal Resolution, IADL=instrumental activities of daily living. MCI=mild cognitive impairment. +For ATTR and Timed IADL lower scores reflect better performance.

Table 14.3. *Effect sizes for piano training relative to music listening across composite outcomes and assessments for the analytic sample overall, among those adherent, and by cognitive status.*

Outcome Measure	d Effect Size			
	Overall (n =198)	Adherent (n =189)	Non-MCI (n =146)	MCI (n =52)
Central auditory processing composite	-0.01	-0.01	0.00	-0.07
Dichotic Digits	-0.06	-0.07	-0.03	-0.14
Dichotic Sentence Identification	0.01	0.01	0.02	-0.07
Time Compressed Speech	-0.01	0.01	0.03	-0.06
Words in noise	0.03	0.03	0.12	0.01
Adaptive Tests of Temporal Resolution composite	0.17	0.20	-0.09	0.24
Cognitive composite	-0.03	-0.03	-0.10	0.08
Trails A	0.03	0.06	0.00	0.43
Trails B	-0.17	-0.20	0.01	-0.54
Digit Symbol Coding	0.08	0.09	0.06	0.26
Test of Everyday Attention - Visual elevator timing subtest	0.02	0.02	0.03	0.44
Test of Everyday Attention - Telephone search time	-0.29	-0.32	0.08	-0.27
Verbal fluency composite	0.05	0.06	0.09	-0.12

Letter fluency	0.00	0.02	0.09	-0.36
Category fluency	0.18	0.20	0.18	0.13
Switching fluency	-0.06	-0.05	-0.07	-0.05
Test of Everyday Attention composite	0.04	0.08	-0.30	-0.02
Visual Elevator accuracy	0.01	0.03	-0.12	-0.19
Dual task decrement	0.10	0.13	-0.18	0.22
Timed Instrumental Activities of Daily Living composite	-0.15	-0.21	0.09	-0.13

Note. MCI=mild cognitive impairment. *d* effect sizes were calculated as pre- to post- change in the piano training condition relative to the music listening condition divided by the baseline standard deviation such that positive values would indicate improvement. Adherent analyses include those who completed 15 or more sessions of the assigned condition.

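### The Section 14 text names the three MCI effect sizes at or above +0.25 but not the three at or below -0.25 in the same column of Table 14.3

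*Combined protocol and SAP*

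**What the plan says.** Section 14 first reports that no three-way interaction of group, time and MCI status was significant (all p > .245) and concludes that MCI status did not moderate the effect. It then turns to effect sizes and finds no improvement overall, among adherent participants, or without MCI. Participants with MCI in the piano arm, however, "showed potential small effect sizes for improvement relative to music listening on Trails A, Digit Symbol Coding, and one subtest of the TEA", with ds of 0.25 or more. The text describes no unfavourable effect size.

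Table 14.3 prints the full set. Its columns are overall, adherent, non-MCI and MCI, and its note defines d as the relative pre-to-post change "divided by the baseline standard deviation such that positive values would indicate improvement". Two of the benefits named in the text read "Trails A 0.03 0.06 0.00 0.43" and "Digit Symbol Coding 0.08 0.09 0.06 0.26". The same table also shows "Trails B -0.17 -0.20 0.01 -0.54" and "Letter fluency 0.00 0.02 0.09 -0.36".

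On stratification, Section 9.6 (Specific Aim 2) says "When an interaction is significant, we will stratify analyses by MCI status and examine effect sizes". Later under the same aim it separately plans effect sizes for every individual measure, by MCI status as well as overall, with no significance condition.

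**The concern.** A threshold applied to one side of a column gives a different impression from the same threshold applied to both sides. Sections 2.2 and 9.2.1 state that the MCI moderation aim has no directional hypothesis, so values of -0.25 or below are as relevant to it as values of +0.25 or above.

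The choice of what to name also affects the content. Section 6.3.5 classes Trails A and Digit Symbol Coding as speed of processing, and Trails B and verbal fluency as executive function. The text therefore mentions apparent gains on two speed measures and is silent on apparent losses on two executive measures. It names Part A of the Trail Making Test and not Part B.

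With null results elsewhere, this is the only sentence in Section 14 that favours piano training over music listening on an outcome. It is the one most likely to be quoted, or used to motivate a trial in MCI.

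**Working it through.** **Inputs.** The MCI column of Table 14.3 (n = 52) has 20 rows: 14 individual tests and 6 composites. Positive means improvement with piano training relative to music listening.

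**Step 1: reproduce the text.** Counting values of +0.25 or more gives three, all individual tests. They match the text; the unnamed TEA subtest is Visual Elevator timing.

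**Step 2: apply the same threshold in the other direction.**

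| At or above +0.25 | d | At or below -0.25 | d |
|---|---|---|---|
| Visual Elevator timing | 0.44 | Trails B | -0.54 |
| Trails A | 0.43 | Letter fluency | -0.36 |
| Digit Symbol Coding | 0.26 | Telephone Search | -0.27 |
| Mean | 0.377 | Mean | -0.390 |

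Mean of the six: (1.13 - 1.17)/6 = -0.007. Of the 14 individual tests, 6 are positive and 8 negative, with mean -0.014.

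**Step 3: could the negative signs be a scaling slip?** The five components of the cognitive composite average (0.43 - 0.54 + 0.26 + 0.44 - 0.27)/5 = 0.064, close to the printed composite of 0.08. With Trails B and Telephone Search reversed, the average would be 1.94/5 = 0.388. The three fluency tests average (-0.36 + 0.13 - 0.05)/3 = -0.093, against a composite of -0.12. The printed signs are plausible, though this does not prove them.

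**Step 4: precision.** Assume 26 per arm, equal SDs at both visits and pre-post correlation r. Then SE(d) = sqrt(2(1 - r)) x sqrt(1/26 + 1/26), the 95% half-width is 1.96 x SE, and the expected number of 14 tests with |d| of 0.25 or more under no effect is 14 x 2(1 - Phi(0.25/SE)).

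| r | SE | Half-width | Expected of 14 |
|---|---|---|---|
| .50 | 0.277 | 0.54 | 5.1 |
| .60 | 0.248 | 0.49 | 4.4 |
| .70 | 0.215 | 0.42 | 3.4 |
| .80 | 0.175 | 0.34 | 2.2 |
| .88 | 0.136 | 0.27 | 0.9 |

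The reliabilities in Section 6.3.5 can stand in for r:

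- Trails A (.53 to .64): half-width 0.46 to 0.53, so +0.43 lies inside.
- Trails B (.54 to .62): 0.47 to 0.52, so -0.54 lies just outside.
- TEA subtests (.59 to .86): 0.29 to 0.49. Telephone Search at -0.27 lies inside throughout; Visual Elevator timing at +0.44 lies outside only if r exceeds about .67.
- Letter fluency (.88): 0.27, so -0.36 lies outside. Different letter sets are used at baseline and post-test, however, which may lower r.
- Digit Symbol Coding: no reliability is given; +0.26 lies inside for every r in the table.

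Precision therefore gives no reason to name the three favourable values and leave out the other three.

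**Step 5: consistency of the rows.** Weighting the subgroups by n = 146 and n = 52:

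- Telephone Search: (146 x 0.08 - 52 x 0.27)/198 = -0.01, against a printed overall value of -0.29.
- Visual Elevator timing: (146 x 0.03 + 52 x 0.44)/198 = 0.14, against a printed 0.02.

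Both printed overall values fall outside the range of their two subgroup values.

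**The case against.** Much can be said for the report.

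- **Nothing is hidden.** A reader might infer that Section 14 suppresses the negative results. It does not: Table 14.3 belongs to Section 14, prints all six values with the sign convention, and is cited in the same paragraph. Only the prose leaves them out.
- **The null is stated.** A reader might infer that a null subgroup result is presented as a finding. The preceding paragraph reports the non-significant interactions and concludes that there was no moderation, and the sentence itself is hedged.
- **The stratification was planned.** A reader might take the significance condition in Section 9.6 to bar any MCI effect size. The later paragraph under the same aim plans these effect sizes for each measure unconditionally.
- **There is a reason to look for gains.** The efficacy hypothesis in Section 2.1 is directional, and Sections 6.3.4 and 9.5 use d = 0.25 as an improvement benchmark.
- **Intervals were not promised here.** Section 9.5 commits to confidence intervals at the interim analysis; Section 9.6 does not for the final individual-measure effect sizes.

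The first three arguments stand and limit the point to the wording of one sentence. The fourth explains where 0.25 comes from, but that benchmark was an interim trigger for changing the number of sessions, not a rule for reading MCI strata. The fifth makes the intervals a recommendation. None of them accounts for naming three values and passing over three of comparable size.

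**Conclusion.** The point holds as a fault of description. The text applies a 0.25 threshold in one direction to a column in which three values pass it each way, the largest is negative (Trails B, -0.54) and the six average about zero. The counts and averages come straight from the table and need no assumption. The table, the stratification and the conclusion on moderation are unaffected.

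Three stronger readings should be resisted.

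- **That the omitted values are uniformly as large as the named ones.** Letter fluency at -0.36 is smaller in size than Trails A and Visual Elevator timing. The two sets are comparable on average (0.39 against 0.38).
- **That piano training harms executive function in MCI.** With half-widths of roughly 0.27 to 0.54, many tests and a non-significant interaction, the data do not show this.
- **That all six values are demonstrably noise.** About 1 to 5 of 14 independent tests would reach the threshold under no effect, so six is near expectation at low correlations and above it at high ones.

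The precision figures rest on an assumed 26 per arm, an assumed range for r and, for the expected counts, independent tests.

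**What to change.** Rewrite the sentence so that the threshold works in both directions: name all six MCI values with their signs, or none. Say beside it that the pattern is mixed and consistent with the non-significant MCI interaction already reported.

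Before restating any values, check the Telephone Search and Visual Elevator timing rows of Table 14.3 against the data. Different baseline SDs in the denominators might explain part of the discrepancy, but each row supplies one of the six values.

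Preferably add 95% confidence intervals to the MCI column, using the actual arm sizes and the observed variance of change in place of the assumptions made here.

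The cost is one or two sentences, a check of two rows and, if adopted, one table column. No planned analysis changes.

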expectations about the assigned condition were significantly related to composite outcomes of CAP and cognition. However, having greater expectations that the randomized condition would positively affect abilities was associated with poorer performance. See Table 2. Additional sensitivity analyses examined if there were differential effects by sex. No significant group-time-sex interactions were evident ($p > .119$), and the pattern of results was the same when analyses were stratified by sex.

Table 14.1. *Participant characteristics by randomized arm and cognitive status.*

Cognitive status	Piano Training		Music Listening	
	Non-MCI	MCI	Non-MCI	MCI
	M (SD)	M (SD)	M (SD)	M (SD)
	n (%)	n (%)	n (%)	n (%)
Age in years	69.1 (5.5)	71.4 (7.1)	69.6 (5.2)	72.1 (5.7)
Education in years	16.0 (2.3)	16.5 (2.2)	16.0 (2.1)	15.4 (2.3)
Sex (% female)	63 (65%)	18 (48%)	58 (59%)	17 (44%)
Music Reading Assessment score (/40)	2.52 (4.31)	2.43 (3.83)	3.42 (5.41)	2.08 (4.29)
Montreal Cognitive Assessment score (/30)	26.6 (2.1)	23.3 (1.4)	26.6 (1.9)	22.8 (1.6)
Geriatric Depression Scale short-form score (/15)	0.9 (1.2)	1.1 (1.1)	0.9 (1.1)	0.6 (0.9)
Pure tone average left ear (dB)+	19.8 (9.4)	20.4 (9.4)	20.9 (10.8)	27.7 (15.9)
Pure tone average right ear (dB)+*	18.6 (10.3)	20.4 (9.9)	22.4 (14.0)	25.8 (11.6)
Visual acuity (logMAR)+*	.04 (.12)	.09 (.15)	.01 (.13)	.01 (.10)
Expectations (rating/7)*	5.4 (1.2)	5.8 (0.8)	4.9 (0.8)	5.3 (0.8)

Note. MCI=mild cognitive impairment. +Lower scores reflect better performance. *Significant differences by randomized group were evident in pure tone average right ear, visual acuity, and expectations ($ps<.01$).

Table 14.2. *The effects of randomization to piano training as compared to music listening from baseline to post-training across composite outcomes of central auditory processing, cognition, and everyday function.*

	Estimate	SE	p	Estimate	SE	p
	ATTR+			Central auditory processing		
Intercept	53.90	1.17	<.001	46.25	0.73	<.001
Group	-2.24	2.37	.346	-1.72	1.49	.249
Time	-2.77	0.68	<.001	2.29	0.36	<.001
Group x time	1.51	1.35	.265	.465	0.71	.515
Hearing	0.12	0.06	.030	-0.63	0.04	<.001
Visual acuity	6.24	4.71	.187	-7.270	3.97	0.07
Expectations	0.79	0.59	.185	-1.20	0.49	.016
	Verbal fluency			Cognition		
Intercept	49.32	0.98	<.001	51.81	0.90	<.001
Group	-1.81	2.00	.367	-2.62	1.84	.157
Time	0.41	0.48	.393	-1.40	0.42	.001
Group x time	-0.29	0.96	.763	0.39	0.84	.638

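### Tables 14.2 and 14.3 print opposite signs for the piano effect on all six composites, and the group coding that would settle which is right is not stated

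*Combined protocol and SAP*

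**What the plan says.** Section 9.6 makes the group x time interaction the Aim 1 estimate. Sections 1.3 and 2.1 name cognition as the primary outcome of interest. Section 14 reports the results in two tables.

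- Table 14.2 gives model estimates under the title "The effects of randomization to piano training as compared to music listening from baseline to post-training across composite outcomes". Its note says "For ATTR and Timed IADL lower scores reflect better performance"; no other composite is flagged. The interaction rows are "Group x time 1.51 1.35 .265 .465 0.71 .515" (ATTR, then CAP), "Group x time -0.29 0.96 .763 0.39 0.84 .638" (verbal fluency, then cognition) and "Group x time -1.53 1.58 .327 -0.40 1.340 .765" (Timed IADL, then TEA).
- Table 14.3 gives d for piano relative to music listening. Its note describes change "divided by the baseline standard deviation such that positive values would indicate improvement". The CAP row, for example, reads "Central auditory processing composite -0.01 -0.01 0.00 -0.07", with the overall sample first.

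The Section 14 text reports that no interaction was significant. It makes no directional statement from Table 14.2's interaction terms. From Table 14.3 it does make one: potential small benefits of piano in participants with MCI on Trails A, Digit Symbol Coding and one TEA subtest. Neither the tables nor the text state which arm was coded as the higher group level, and no arm-level composite means are given.

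**The concern.** The two tables report the same contrast on the same outcomes, so their signs should agree apart from small differences due to covariate adjustment. Taken at face value they disagree in every row. A reader of Table 14.2 would record a point estimate for cognition slightly in favour of piano; a reader of Table 14.3 would record one slightly against. Anyone who takes a confidence interval or an input for pooling from the wrong table carries the wrong sign forward. If Table 14.3 is the reversed one, the statement about MCI participants is reversed with it.

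**Working it through.** **Inputs.** Group x time estimates and SEs come from Table 14.2, and overall d values from Table 14.3.

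**Scoring and time direction.** The Section 14 text reads the time effects for ATTR (-2.77) and CAP (+2.29) as improvement, and those for cognition (-1.40) and TEA (-8.61) as decline. So time runs from baseline to post-test, ATTR is lower-is-better, and CAP, cognition and TEA are higher-is-better, as the note implies.

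**Printed p-values.** From estimate/SE with a t distribution on 196 df (an assumption), recomputed against printed: ATTR .265 / .265; CAP .513 / .515; verbal fluency .763 / .763; cognition .643 / .638; Timed IADL .334 / .327; TEA .766 / .765. Five agree once rounding of the printed inputs is allowed for. Timed IADL does not: its rounding range is .331 to .337. A two-sided p-value is blind to sign, so this check cannot show which table is right.

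**Sign comparison.** Benefit = estimate, multiplied by -1 for ATTR and Timed IADL. Dividing by 10 assumes T-score-like units. The SD is not stated; five of the six intercepts lie between 46 and 54, but TEA's is 62.34.

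| Composite | Estimate | Benefit / 10 | Overall d | Signs |
|---|---|---|---|---|
| ATTR | +1.51 | -0.15 | +0.17 | opposite |
| CAP | +0.465 | +0.05 | -0.01 | opposite |
| Verbal fluency | -0.29 | -0.03 | +0.05 | opposite |
| Cognition | +0.39 | +0.04 | -0.03 | opposite |
| Timed IADL | -1.53 | +0.15 | -0.15 | opposite |
| TEA | -0.40 | -0.04 | +0.04 | opposite |

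The signs need no scale assumption. The sizes do: with an SD of 8 to 12, cognition in Table 14.2 is +0.05 to +0.03, and the ATTR and Timed IADL sizes are about 0.19 to 0.13.

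**One cause or several?** With an SD of 10, the mean absolute gap between the benefit and d columns is 0.151 as printed. It falls to 0.015 if the signs of one column are reversed, and the largest remaining gap is 0.037 (CAP). The correlation between the columns is -0.99.

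**Alternative explanation.** If d had been left unreversed for the two lower-is-better outcomes, ATTR and Timed IADL would agree in sign. CAP, verbal fluency, cognition and TEA would still conflict.

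**Effect on the interval.** For cognition, 0.39 ± 1.96 × 0.84 gives -1.26 to 2.04. If the sign is reversed it becomes -2.04 to 1.26.

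**Internal check of Table 14.3.** The overall d lies outside both subgroup values (non-MCI, MCI) for TEA (0.04 against -0.30 and -0.02) and for Timed IADL (-0.15 against 0.09 and -0.13). The n-weighted subgroup means are (146 × -0.30 + 52 × -0.02)/198 = -0.23 and (146 × 0.09 + 52 × -0.13)/198 = +0.03. Different subgroup SDs could explain part of this, but the rows need checking.

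**The case against.** The strongest reply is that Table 14.2's title names a comparison and is not a statement of coding. In all six models the group x time SE is about twice the time SE (for example 0.84 against 0.42 for cognition, 1.35 against 0.68 for ATTR). That fits a centred group contrast, whose sign depends on an unstated level order. Table 14.3 does state its convention. On this view the defect is an unlabelled contrast. That stands as a description of the likely cause, but a reader has only the title and note to go by, and these give the wrong direction if music listening was the higher level.

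Other points also stand. Four rows, including cognition, are within about 0.05 SD of zero in both tables. Table 14.2 is covariate-adjusted, while Table 14.3 is described as change over baseline SD, so one mismatch near zero, such as CAP at d = -0.01, would prove little. The weight rests on six mirrored rows. The text mentions supplementary plots that may show direction; they are not in the documents.

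A reader might infer that the trial's finding is in doubt, or that the direction of effect cannot be recovered. The documents support neither. The text claims only non-significance, which no sign change touches, and the coding and arm means should settle the direction. A reader might also take the mostly reproducible p-values as proof that the estimates are correctly printed. They are not: one falls outside rounding, and none can detect a reversed sign.

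**Conclusion.** The point holds as an inconsistency between two results tables. Under their own title and notes, Tables 14.2 and 14.3 oppose each other in sign for six of six composites, so the Aim 1 point estimates and their intervals have the wrong sign in one of them. The near-mirror sizes, which assume an SD of about 10, point to one cause. Music listening coded as the higher group in Table 14.2 is the most likely; a reversal throughout Table 14.3 is the other candidate. The documents cannot separate them.

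The swing is about 0.3 SD for ATTR and Timed IADL and 0.06 to 0.08 SD for the other four, including cognition. Every interaction p-value in Table 14.2 is .265 or higher and the null conclusion is unaffected. The statement about MCI participants is at risk only if Table 14.3 is the reversed table. This should be fixed, but it does not threaten the trial's main conclusion.

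**What to change.** 1. Check the group coding used in the models against arm-level baseline and post-test composite means, and report those means.
2. If Table 14.2 is music listening minus piano, re-express its Group and Group x time rows as piano minus music listening. If Table 14.3 is the reversed one, correct it and the MCI statement in the Section 14 text.
3. State the group coding, the time coding and the better direction for each composite in the table notes.
4. At the same time, recheck the TEA and Timed IADL rows of Table 14.3 against their subgroup values, and the Timed IADL p-value in Table 14.2 (.327 printed, about .33 to .34 from estimate/SE).

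No new data or tests are needed, and a sign change leaves the p-values as they are. The cost is a coding check and at least one reissued table. Because of step 4, recoding a single variable may not be enough.

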5.8 Adherence Assessment

To address the study aims, we will use intent-to-treat analyses as detailed in section 9.5 below. We will report the percent of participants who were adherent to the assigned piano training or music instruction exercises. Participants will be considered adherent if they complete at least 80% of the assigned sessions (at least 16 of 20 sessions). The Research Assistant Trainers will record dates that participants attended in-lab training. Participants will be allowed up to 15 weeks to complete the assigned exercises between baseline and post-test.

Primary data analyses will be intent-to-treat. Sensitivity analyses will further examine effects of piano training relative to music instruction among those who were adherent (i.e., who completed 16 or more hours) in both conditions.

08/08/2018

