Specific Aim 1: To examine the efficacy of piano training to improve CAP, cognition, and everyday function among older adults. We will compare changes in performance for piano training relative to control across the two measurement points (baseline, immediate post-test). We will use the PCA-derived composites of CAP and cognition, and everyday functioning as outcomes. We will use repeated measures analyses of variance within the mixed effects models, examining group as the between-subjects factor and time as the within-subjects factor. The group x time interaction will indicate whether the participants randomized to piano training change at differential rates over time relative to those randomized to the control group. This output will be obtained for each of the composite outcomes (CAP, cognition, and functional abilities). For aim 1 analyses and the composite outcomes of CAP, cognition, and everyday function, we will apply Holm-Bonferroni adjustments¹²⁵ to reduce Type I error. Specifically, the Holm-Bonferroni procedure uses a step-down process whereby p-values are sorted from lowest to highest, then the lowest p-value is used in its raw version, the second lowest p-value is multiplied by two, the third lowest p-value is multiplied by three and so on until the adjusted

p-value reaches or exceeds the pre-specified threshold for statistical significance, in our case a two-tailed p value of .05.

Intent-To-Treat Approach. We expect that some participants will not complete their intended followup according to the protocol for a variety of reasons, generating missing values. Intent-to-treat (ITT) analysis has become a widely accepted method for dealing with this issue. To maximize available information, we will employ statistical techniques that allow for the inclusion of missing data. Specifically, we will use linear mixed effects models to analyze data. This advanced analytical method allows for the inclusion of participants with missing data, so long as data are missing at random and offers flexibility with regard to the specification of the variance/covariance structure, which often leads to improved fit of the analytical model to the actual data. If there is non-ignorable missing data, we will apply pattern-mixture mixed effects models to assess the sensitivity of our findings with regard to missing data¹²⁶.

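### Table 14.3's effect sizes are unlabelled both-visit results for 198 people, about 69–74% of the sample, and Table 14.2 does not show that it kept people without a post-test

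*Combined protocol and SAP*

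**What the plan says.** **The plan.** Section 5.8 states: "Primary data analyses will be intent-to-treat". Section 9.6 gives the means, a linear mixed model: "This advanced analytical method allows for the inclusion of participants with missing data, so long as data are missing at random". The Aim 1 test is the group-by-time interaction: "We will use repeated measures analyses of variance within the mixed effects models, examining group as the between-subjects factor and time as the within-subjects factor". Under Aim 2, Section 9.6 adds a separate descriptive output: "we will calculate and report effect sizes for pre-to-post change of piano training relative to controls for each individual measure", for the whole sample, by MCI status and among adherent participants. Sections 5.7.1 and 8 keep data collected before a disqualifying event.

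**The results.** Section 14 first uses the word primary for the planned test: "In the primary analyses, we examined whether performance changed differentially by random assignment across composite outcomes from baseline to post-test". Those results are in Table 14.2, without an n. The models adjust for hearing, visual acuity and expectations. The effect-size paragraph then uses the word again: "Improvements were not evident in the primary analyses, adherent analyses, or the subsample without MCI". These labels match the columns of Table 14.3, whose title says that it gives effect sizes "across composite outcomes and assessments for the analytic sample overall, among those adherent, and by cognitive status": overall (n=198), adherent (n=189), non-MCI (n=146) and MCI (n=52). The table note defines d as pre-to-post change in one arm relative to the other, divided by the baseline SD. Section 14 also reports that 76% of those randomised completed the post-test and that 19 people were excluded from analyses.

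**The concern.** An observed change needs both visits, so Table 14.3 leaves out everyone without a post-test. A raw change comparison in the remaining people is unbiased only if leaving is unrelated to change, or related to it in the same way in both arms. The plan's mixed model needs less. Under missing at random it uses the leavers' baseline scores, and it corrects for dropout that depends on baseline differently in the two arms.

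This matters because d is the figure a reader will take as the size of the null result. The MCI column also carries the only positive statement in Section 14: possible small benefits, with d of at least 0.25, on Trails A, Digit Symbol Coding and one Test of Everyday Attention (TEA) subtest. Neither table lets a reader confirm that an efficacy estimate comes from the sample the plan promised.

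**Working it through.** **1. Reproduce the n.** Table 14.3: 146 + 52 = 198.

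**2. Denominator.** The baseline tests in Section 14 have 266 error degrees of freedom for two groups, so N = 266 + 2 = 268 (derived, not stated).
- 198/268 = 73.9%, leaving out 70 people.
- If the 19 exclusions are not among the 268: 268 + 19 = 287, and 198/287 = 69.0%.
- The stated 76% completion does not settle it. It fits about 204/268 (76.1%), or (198 + 19)/287 = 217/287 = 75.6%.

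**3. By cognitive status.** Sex counts divided by percentages in Table 14.1 give approximate group sizes.
- MCI: 18/0.48 + 17/0.44 = 37.5 + 38.6, about 76. Retained: 52/76 = 68%.
- Non-MCI: 63/0.65 + 58/0.59 = 96.9 + 98.3, about 195. Retained: 146/195 = 75%.
- These sum to about 271, not 268, so they are approximate.

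**4. What Table 14.2 can have kept.** Expectations are collected at sessions 17–20 or at the start of the post-test (Sections 6.1 and 6.1.2). The expectations test has 214 error degrees of freedom, so 216 people have a rating: 216/268 = 80.6%. Unless ratings were imputed, which is not stated, at most 216 people enter these models, and most early leavers drop out of them.

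**5. Possible bias in d.** Let r be the baseline to post-test correlation. Suppose selective loss leaves the arms' both-visit baseline means δ SD apart. Post-test means then differ by rδ, so the change contrast is off by (1 − r)δ in size. With δ = 0.2 (an assumption; the documents give no figure):

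| r | .5 | .6 | .7 | .8 |
|---|---|---|---|---|
| Bias (SD) | 0.10 | 0.08 | 0.06 | 0.04 |

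**6. Precision.** With equal SDs, the per-arm variance of mean change is 2(1 − r)/n_c for n_c complete pairs. With baseline-only people included it is [(1 − r²) + (1 − r)²(n_c/n)]/n_c. At n_c/n = .739:

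| r | .5 | .6 | .7 | .8 |
|---|---|---|---|---|
| Variance ratio | .935 | .948 | .961 | .974 |

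The variance falls by about 3–7%.

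**7. Cross-check.** Divide the Table 14.2 group-by-time estimates by 10 (assuming composites scaled to SD 10) and sign them so that positive favours piano. Group coding is not stated; this choice makes all six signs agree.

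| Composite | Model/10 | Table 14.3 d |
|---|---|---|
| Adaptive Tests of Temporal Resolution | 0.15 | 0.17 |
| Central auditory processing | −0.05 | −0.01 |
| Verbal fluency | 0.03 | 0.05 |
| Cognition | −0.04 | −0.03 |
| Timed IADL | −0.15 | −0.15 |
| TEA | 0.04 | 0.04 |

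All agree within 0.04.

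**The case against.** The strongest reply is that nothing was substituted. A reader might infer that Section 14 replaced the intent-to-treat primary analysis with a completer analysis. The documents do not support that. The term primary is attached first and mainly to the planned interaction test, and the n behind Table 14.2 is unknown rather than shown to be 198. Nor is Table 14.3 a departure from the plan, since Section 9.6 planned pre-to-post effect sizes. The ingredients are also disclosed: the 76% completion, the 19 exclusions, the n in each column and the definition of d. The flow chart and Supplementary Table B are not in the text reviewed and may give further counts. All of this stands.

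The size is modest too. The 0.2 SD imbalance is assumed. On the SD 10 scaling, the cognition interaction has a standard error of 0.84/10 = 0.084. With 99 per arm, 4(1 − r)/99 = 0.084² gives r of about .83. The bias is then 0.17 × 0.2, about 0.035, under half a standard error.

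Two parts of the reply are weaker. The agreement in step 7 covers only the six overall composites, not the MCI column. It is also little reassurance if Table 14.2 itself ran on a reduced sample, which step 4 makes plausible. And simply refitting the reported model to everyone randomised would not help, because the expectations covariate would still remove most early leavers.

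**Conclusion.** The concern holds as a matter of labelling and estimation. It does not show that the primary analysis was replaced. Table 14.3 rests on 198 people with both assessments, about 69–74% of the baseline or randomised sample. The table does not say so, and its estimates need a stronger missing-data condition than the plan's. The documents do not show whether the Table 14.2 models kept baseline-only participants.

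The expected shift is 0.04 to 0.10 SD for r from .8 to .5, given an assumed 0.2 SD imbalance from differential dropout. A reader might go further and doubt the null result. The figures do not support that: all the interaction tests are non-significant, and the overall composites agree within 0.04 if the SD is 10, so the overall null result probably stands. The point matters most for the MCI effect sizes, which rest on 52 of about 76 people, carry no intervals and support the only positive statement. The inference that these are both-visit results comes from the definition of d and the n. The 268 comes from degrees of freedom.

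**What to change.** - Derive the overall and by-MCI effect sizes from the Aim 1 and Aim 2 mixed-model contrasts fitted to everyone randomised: estimated difference in change divided by baseline SD, with 95% confidence intervals.
- Include the pre-event data of the 19 excluded participants, as Sections 5.7.1 and 8 allow. Hospitalisation as such (8 of the 19) is not an event listed in either section, so the stated exclusions and those sections must be reconciled.
- Leave expectations out of this model, so that early leavers stay in, and show the expectations-adjusted model as a sensitivity analysis. Section 9.6's p < .1 covariate rule brings expectations in, so record the omission as a dated deviation with its reason.
- State the n per arm at each visit for Tables 14.2 and 14.3.
- Label the n=198 figures, and their MCI and non-MCI columns, as participants with both assessments, and stop calling the overall column primary.

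The cost is a re-run on data already held and new table labels. The downside is that model-based effect sizes are slightly less simple to describe than raw changes.
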